## **Biochemical measurements**

Respondents will be advised not to have any meals before the measures. A blood sample of approximately 5 milliliters will be collected in the morning after a 12-hour overnight fast

from each participant and analyzed using the COBAS 6000 Analyser Series at Mulago National Referral Hospital Department of Clinical Chemistry Laboratory to assess fasting blood glucose, total cholesterol, HDL-cholesterol and triglycerides.

#### **Physical measurements:**

Anthropometry: Body weight will be measured to the nearest 0.01 kg with a portable electronic scale (Seca). Height will be measured to the nearest 0.5 cm without shoes while standing on a level, hard surface using a calibrated stadiometer. Body mass index (BMI) will be computed from body weight and height measurements.

Waist circumference will be measured to the nearest 0.1 cm using a non-stretchable standard tape measure. The measurements will be taken with individuals in light clothing. The tape will be placed just above the uppermost lateral border of the right ilium, at the end of a normal expiration. WC will be taken by female nurses and female medical students.

Blood pressure will be taken using Omron digital blood pressure monitor at rest.

#### Data management

All the data collected in the field will be entered in ODK tool embedded with skip patterns and constraints to ensure data quality and reduce bias. The investigator will cross-check all data at the end of each day and any errors discovered will be corrected immediately or by the research assistants the following day as appropriate. Quantitative data (ODK data) will be downloaded from server and exported to stata version 14 for cleaning.

#### **Data Analysis**

The data for participants who attend less than 60 % of their respective intervention sessions will be excluded from analyses.

Participants with attendance rates below 60% in the intervention sessions will not be included in the analyses.

The analyses will be conducted using Stata statistical software (SE/ 14.0, StataCorp, College Station, TX, USA. Variables will be expressed using descriptive analysis (means and SD). The baseline information for both comparison and intervention groups will be statistically compared regarding all influencing factors at baseline and end line (12 weeks). The chi-square test will analyse for differences in categorical outcomes, including baseline study characteristics, metabolic risk factors (waist circumference (WC), blood pressure (BP), triglycerides, fasting blood sugar(FBS), and high-density lipoprotein (HDL) Cholesterol),

and other factors including dietary habits such as fruits and vegetable intake, and food groups consumed. Behaviours, including smoking, alcohol intake, and physical activity, will also be analysed.

The Student T test for independent samples and variance analysis (ANOVA) will compare cardio-metabolic parameters (and their variations - to find any differences between findings) between the intervention group and the comparison group at the baseline and end of the intervention (after-before).

A 2 factor (2 x 2; group x time) repeated measures analysis of variance (ANOVA) will be performed for each dependent variable and a 1-way ANOVA will be used to assess the significance of differences between groups on the dependent variables assessed. Tukey's post hoc analysis will be performed if there is a significant finding. The T test for paired data will be applied to investigate within –group variable variations (after-before). Statistical significance will be set at p < 0.05.

Linear relationships will be estimated using Pearson correlation (crude model) to examine the associations between changes in variables, expressed as percentage of change ((endpoint - baseline value)/baseline value × 100). A multilevel generalized linear mixed model (GLMM) will be performed to identify the contribution of changes in time /round (baseline, end-line) and group (control, intervention) to changes in metabolic parameters (BP, WC, HDLC, FBS and Triglycerides) independent of other factors (education level, age, occupation etc). The model allows for the analysis of data with repeated measures, particularly baseline and end-line measurements for each individual. It also assesses the effects of the intervention and accounts for the correlation between observations within individuals due to repeated measures, as well as the clustering of individuals within the control and intervention groups.

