#### Package of the group motivation interviewing sessions

3 sessions of group motivation interviewing (MI) will be held monthly over 3 months in groups of approximately 12 participants covering various topics, including goal setting, factors that motivate lifestyle and behavioural change, relapse and its management, coping strategies and support, eating habits at various settings. Discussions will be held on relevant topics using MI techniques.

**Comparison:** In the comparison group, participants with MetS will be subjected to only usual standard of care with no specific individualized interventions. This will include referral of the participants to the usual health care facilities for management of their conditions as per the existing routine health facilities protocols. This is for purposes of controlling for possible changes in outcome variable due to other influences or behaviours.

Effort will be undertaken to reduce non-adherence in intervention group through evaluating questionnaires and meeting attendance, use of paper and phone reminders, provision of information about study objectives and planned meeting schedules, and reinforcement of the need for compliance during follow up meetings.

 Table 2: Summary table for the intervention and non-intervention arms

No.	Intervention arm	Control arm
1.	Participants =60 women of reproductive age with MetS divided into 6 groups at baseline	Participants =60 women of reproductive age with MetS (no groups) at base line
2.	Intervention and duration: One hour of weekly group nutrition education seminar sessions offered for 12 sessions in 3 months and One hour of monthly group motivational interviewing sessions offered for 3 sessions undertaken for 3 months.	Duration of follow up: Usual standard of care in nutrition education varies depending on either inpatient or outpatient setting
	Behavioral change for dietary intake and physical activity enhanced by, motivation interviewing	Usual standard of care in nutrition education and counselling. There is limited or no focus on Motivational Interviewing for behavioural cchange
	Delivered by: Nutritionists and health workers using a tailor made curricular guide and materials for MetS	Delivered by: Nutritionists and health workers using nutrition guides and materials for management of malnutrition (under and over nutrition)

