#### 3.6 Outcomes of interest:

#### **Primary outcome**

The primary outcome will be the between–group change in MetS prevalence after 3 months from start of intervention.

The 2009 Joint Interim Statement (JIS) will be used to diagnose MetS, defined as the presence of  $\geq$  3 of the following 5 factors: increased WC (women:  $\geq$  80 cm), low HDL-C (women: <50 mg/dl (1.3 mmol/l) or treatment of low HDL-C), Hypertriglyceridemia  $\geq$ 150 mg/dl (1.7 mmol/l) or treatment, elevated BP (systolic BP  $\geq$  130 mmHg and/ or diastolic  $\geq$ 85

mmHg or treatment for hypertension) and elevated fasting blood sugar (FPG  $\geq$  100 mg/dl (5.6 mmol/l) or diabetes mellitus or treatment[3]

The European cutoffs for waist circumference will be used as recommended by WHO because of the unavailability of population/country specific WC cutoffs for sub-Saharan Africans [3] or Uganda.

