#### **3.7 Sample size Determination**

#### Sample size for participants with Metabolic Syndrome (Primary outcome variable)

Using Power analysis computation of sample size with G.Power 3.1.9.4 software. The estimates will be based on a significance level of 5% and power of 80% to detect a difference between-group of 0.20 in MetS prevalence after 3 months intervention. A sample size of 98 is obtained. After accounting for design effect the sample size is 104. Assuming a dropout rate and failure to consent rate of 10%, 120 participants will be needed in total. 60 participants in the intervention and 60 in the non- intervention groups.

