#### **Randomization: Sequence generation**

The randomization procedure will be automatically performed by a biostatistician to minimize the differences between the two groups for all stratifying variables. Using a computer random number generator a randomisation list of permuted blocks of size 8 with an allocation ratio of 1:1 will be generated. Then the participants will be randomly allocated to either the intervention arm (60) or the control group (60) and followed up for 3 months.

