# 3.9 Data Collection and Management:3.9.1 Data collection tool

To ensure consistency and minimization of errors in the data collected, standardized methods of data management will be used by the study team.

**Data Collection Procedures:** Base line data will be collected from study participants in the intervention and control group. This will be before the introduction of the intervention. At baseline data collection, informed consent, questionnaires on comprehensive medical history, dietary intake, smoking and alcohol intake, medication use, physical activity, anthropometry, BP, FBS and lipid profile tests will be undertaken for all participants.

After the introduction of the intervention, data will be collected serially from study participants in the intervention arm on selected variables before the group sessions to monitor adherence of participants to the intervention. Final end-line data similar to data collected at baseline will be collected in both the intervention and non-intervention arms. In control group, the participants who have baseline data will be considered in analysis for comparison purposes.

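### Excluding intervention women who attend under 60% of sessions is a one-sided, post-randomisation filter that breaks the randomised primary comparison and can bias it, probably but not certainly towards the intervention

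*Protocol*

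**What the plan says.** The Data Analysis text in section 3.9 opens with the rule "The data for participants who attend less than 60 % of their respective intervention sessions will be excluded from analyses" and restates it at once: "Participants with attendance rates below 60% in the intervention sessions will not be included in the analyses". Neither sentence mentions a per-protocol, secondary or sensitivity analysis. All the tests and models that follow come under it.

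The two arms differ in what they could attend. Table 2 in section 3.3 gives the intervention arm "One hour of weekly group nutrition education seminar sessions offered for 12 sessions in 3 months", plus three monthly motivational interviewing sessions. In the comparison arm, "participants with MetS will be subjected to only usual standard of care with no specific individualized interventions". The data collection text in section 3.9.1 says of controls: "In control group, the participants who have baseline data will be considered in analysis for comparison purposes".

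Allocation is individual and 1:1: "Then the participants will be randomly allocated to either the intervention arm (60) or the control group (60) and followed up for 3 months". The primary outcome (section 3.6) is the between-group "change in MetS prevalence after 3 months from start of intervention". Section 3.7 targets a difference of 0.20 and allows 10% for dropout and refusal of consent. The protocol describes no intention-to-treat or other as-randomised analysis.

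**The concern.** Randomisation makes the arms comparable only if women are analysed in the arm assigned, whatever they do afterwards. Attendance is behaviour after allocation. Women who would attend poorly are present in both arms, but this rule removes them from one arm only. The comparison is then between a selected intervention group and an unselected control group.

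Willingness to attend plausibly goes with motivation to change diet and activity. The protocol itself links the two, since section 3.8 provides counselling to motivate attendance. If such women are also more likely to lose their metabolic syndrome (MetS) diagnosis without the programme, the rule produces a difference even when the programme does nothing. The planned adjustment for age, education and occupation would not recover unmeasured motivation.

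**Working it through.** **Step 1: who can be excluded.**

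| | Intervention | Control |
|---|---|---|
| Study sessions | 12 weekly and 3 monthly, plus physical activity sessions | none |
| Attendance condition for analysis | at least 60% | none possible |
| Other stated condition | – | has baseline data |

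The attendance filter can act in one arm only, and nothing in the text exempts the primary outcome.

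**Step 2: inputs for the size.** From the protocol: 60 per arm, 10% allowance, target difference 0.20, significance level 5%. After the allowance, 60 × 0.90 = 54 per arm. Every participant has MetS at entry, so a difference in prevalence at 3 months is a difference in remission with the sign reversed. Assumed, because the documents do not give them: the share of low attenders p, and the remission rates of low attenders (r_low) and of other women (r_high).

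**Step 3: bias when the programme has no effect.** The control arm remits at p·r_low + (1 − p)·r_high. The filtered intervention arm remits at r_high. The difference is

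bias = r_high − [p·r_low + (1 − p)·r_high] = p × (r_high − r_low).

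**Step 4: type I error.** This comes from simulating trials with no effect: 54 per arm, the same share of low attenders in both arms, exclusion in the intervention arm only, and a two-sided pooled two-proportion z test. Repeat runs differ by a few tenths of a point.

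| p | r_low vs r_high | Bias (points) | Type I error |
|---|---|---|---|
| 30% | 25% vs 25% | 0.30 × 0 = 0 | 5.1% |
| 10% | 15% vs 25% | 0.10 × 10 = +1.0 | 5.4% |
| 30% | 20% vs 25% | 0.30 × 5 = +1.5 | 5.6% |
| 20% | 15% vs 25% | 0.20 × 10 = +2.0 | 5.7% |
| 30% | 5% vs 25% | 0.30 × 20 = +6.0 | about 11% |
| 40% | 5% vs 35% | 0.40 × 30 = +12.0 | about 23% |

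Positive values favour the intervention. As shares of the 20-point target, 1, 6 and 12 points are 5%, 30% and 60%. The sign can reverse: with 30% low attenders remitting at 35% against 25%, the bias is 0.30 × (−10) = −3.0 points.

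A separate normal-approximation calculation agrees in pattern. It assumed 70% MetS prevalence at 3 months and 60 controls against 60(1 − p). A bias of 1 point (p = 10%, gap 10 points) gave 5.2%, 6 points (30%, 20) gave 9.9%, and 12 points (40%, 30) gave 22.6%.

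**Step 5: numbers analysed.** Section 3.7 needs 104 in total after the design effect, or 52 per arm. The 10% allowance leaves 54, a margin of two women. Low-attendance exclusions beyond those already lost to dropout or refusal would reduce the intervention arm further. If 30% of the 54 were excluded, 54 × 0.70 ≈ 38 would remain. That figure assumes no overlap with dropouts, so it is a worst case for that share.

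**The case against.** Several points on the other side have force.

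- A reader might infer that the rule certainly favours the intervention. The documents do not support that. They give no prognosis for low attenders; with equal prognosis there is no bias, and women who skip sessions because they are doing well would reverse it.
- A reader might take 11% or 23% as the trial's type I error. Those cases assume that low attenders remit at a fifth or a seventh of the others' rate. Milder gaps leave the error below 6%.
- Sections 3.3 and 3.8 plan reminders, attendance registers, weekend sessions and motivational counselling. These make 30 to 40% low attendance less likely, although they do not change what the rule does.
- Controls are not free of losses. An endline comparison needs endline data, so control dropouts are lost too. The asymmetry concerns attendance alone.
- A woman who drops out early also fails the 60% threshold, so attendance exclusions and the 10% allowance overlap in part.
- A statistical analysis plan may exist and define another set. This helps little: the protocol already fixes the exclusion, so such a plan would either carry it forward or contradict it.

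These points limit the size and direction that can be claimed. They do not touch the structure: a one-arm exclusion on behaviour after randomisation, applied to the primary comparison.

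**Conclusion.** The point holds and should be corrected before analysis. As written, the plan replaces the randomised comparison with one between selected intervention women and controls not selected on attendance, and it offers no as-randomised analysis beside it. That conclusion rests on the text alone and needs no assumed figure.

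The size is illustrative. It runs from no bias under equal prognosis, through 1 to 2 points for mild gaps, to 6 and 12 points for the wider gaps in the table. A direction towards the intervention is the likelier one, on the assumption that poor attenders are less motivated and do worse; the documents do not establish it. Further shrinkage of the intervention arm is possible, by an amount that depends on the share of low attenders and its overlap with dropout.

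**What to change.** Delete both 60% sentences from Data Analysis. State that the primary analysis includes all randomised women who consent, in the arm assigned and regardless of attendance. Endline should be sought from all of them in both arms, with a stated rule for missing endline data. The restriction to consenting women is needed because the allocation concealment text takes consent after randomisation, so women who refuse cannot be measured. Report those refusals by arm, since they are also a loss after randomisation.

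Keep the 60% threshold only for a labelled supplementary analysis, either per-protocol or complier-average. Say there which sessions count: 60% of the 12 weekly sessions is 7.2, and 60% of 15 (with the three monthly sessions) is 9.

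The cost is a wording change plus the effort of following low attenders to endline. Endline collection in both arms is already planned in section 3.9.1. The estimate may be smaller: if attenders gain 0.20 and low attenders nothing, the as-randomised difference is 0.20 × (1 − p), which is 0.18, 0.16, 0.14 or 0.12 for 10%, 20%, 30% or 40% low attenders.

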#### Secondary outcomes

The secondary outcome will be the within - and between group variations in each of the following variable measured.

- dietary habits and behaviors (salt intake, fruits and vegetables intake, fat intake,
- anthropometric (weight, WC and BMI)
- cardio-metabolic (hypertension, blood glucose, triglycerides, HDL)
- nutrition knowledge
- lifestyle (physical activity, alcohol intake, cigarette smoking)

Mean change in parameters across the comparison and intervention groups will be determined. The measurement of the outcomes will be conducted before and at the end of the activities to determine the effect of the intervention.

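### No listed between-arm analysis adjusts for the outcome's own baseline value, so precision is lost on the continuous secondary outcomes, mainly diet, activity and knowledge

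*Protocol*

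**What the plan says.** Section 3.6 (Secondary outcomes) lists dietary habits, weight, waist circumference and BMI, the cardio-metabolic measures, nutrition knowledge, and lifestyle (activity, alcohol, smoking). It gives one summary for them: "Mean change in parameters across the comparison and intervention groups will be determined".

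The Data Analysis section of 3.9 then lists several between-arm methods:

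- The repeated-measures analysis: "A 2 factor (2 x 2; group x time) repeated measures analysis of variance (ANOVA) will be performed for each dependent variable".
- A one-way ANOVA between groups on the same dependent variables.
- An independent-samples t test on cardio-metabolic parameters and their before-after variation.
- Chi-square tests for categorical outcomes, among which dietary habits are mentioned. Smoking, alcohol and physical activity are to be analysed as well, with no test named.
- A multilevel generalized linear mixed model whose outcomes are given as "changes in metabolic parameters (BP, WC, HDLC, FBS and Triglycerides". Education, age and occupation are examples of the factors adjusted for. Baseline and end-line are the two levels of time, so the baseline measurement is a response in this model.

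Baseline values are available. The data collection procedures in 3.9.1 cover diet, activity, smoking, alcohol, anthropometry, blood pressure, glucose and lipids in all participants before the intervention. The Project Summary adds knowledge at baseline and end line.

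**The concern.** A change score subtracts the whole baseline value, which fixes the baseline slope at 1. When the baseline to end-line correlation is below 0.5, that adds more noise than it removes, and the comparison is less precise than one that ignores baseline. An end-line comparison makes the opposite choice and fixes the slope at 0. A model that estimates the slope is, in large samples, never less precise than either.

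The secondary objective in 2.2.2 names dietary intake and physical activity alongside the five MetS components. The trial has 120 women and is sized only for MetS prevalence, so precision on these outcomes is whatever the analysis can extract. A real effect on behaviour could be missed although the data that would sharpen the estimate are already collected.

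**Working it through.** **The plan's own figures.** The protocol states no precision or power for any secondary outcome, so there is nothing of that kind to reproduce. Section 3.7 concerns the primary outcome only: "significance level of 5% and power of 80% to detect a difference between-group of 0.20 in MetS prevalence after 3 months intervention", giving 98, then 104 after the design effect, then 120. This point disputes none of those numbers. They are used only to set a number per arm: 60 less the stated 10% is 54.

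**Step 1: the repeated-measures ANOVA and the mixed model are change-score comparisons.** With two time points, the group-by-time contrast is (end-line minus baseline in one arm) minus the same in the other. That is the difference in mean change, and its test is the t test on change. A mixed model with free group, time and group-by-time terms gives the same contrast. (The protocol does not write out the model terms, so this form is assumed.) One simulated data set with 54 per arm and rho 0.5 confirmed it:

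- change-score t = -1.905; mixed-model interaction t = -1.905, SE 0.181
- mixed model with a time-constant covariate such as age added: same estimate, SE still 0.181
- end-line regressed on arm plus baseline value: SE 0.169

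Adjusting for age, education or occupation therefore does not replace adjusting for baseline.

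**Step 2: variances.** Take equal SD (set to 1) at both times and correlation rho. The variance of the between-arm estimate is proportional to:

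- change score: 2(1-rho)
- end-line only: 1
- baseline-adjusted: 1-rho²

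Adjusted over change is (1-rho²)/[2(1-rho)] = (1+rho)/2. Its inverse is the factor by which a change-score analysis needs more women for the same precision.

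**Step 3: numbers.** Rho is not in the protocol, so a range is assumed. The last column is the change-score power for an effect that the adjusted analysis would detect with 80% power (two-sided 5%): Phi(2.80 × sqrt((1+rho)/2) - 1.96). The number per arm cancels from this formula.

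| rho (assumed) | change | end-line | adjusted | adjusted/change | women needed with change score | change-score power |
|---|---|---|---|---|---|---|
| 0.3 | 1.40 | 1 | 0.91 | 0.65 | ×1.54 | 62% |
| 0.5 | 1.00 | 1 | 0.75 | 0.75 | ×1.33 | 68% |
| 0.7 | 0.60 | 1 | 0.51 | 0.85 | ×1.18 | 73% |
| 0.9 | 0.20 | 1 | 0.19 | 0.95 | ×1.05 | 78% |

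For a fixed, assumed effect of 0.5 SD with 54 independent women per arm, power goes from 59% (change) to 78% (adjusted) at rho 0.3, from 74% to 85% at 0.5, and from 92% to 95% at 0.7. It is about 100% for both at 0.9.

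**Step 4: the other listed tests.** If the one-way ANOVA is run on end-line values, the end-line column applies. It matches the change score at rho 0.5 and is far worse at 0.9 (1 against 0.19 for the adjusted analysis). A chi-square on end-line categories also leaves baseline status unused.

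**The case against.** The strongest reply is that nothing here is invalid. Allocation is random and 1:1, so a change-score comparison is unbiased and keeps its type I error. The primary outcome is untouched, and choosing baseline adjustment is good practice rather than the correction of an error. All of that stands. Detail on covariates may also sit in an unseen analysis plan. But the protocol does prescribe specific tests for these outcomes, so this is a comment on a stated method, not on a missing one.

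The size of the loss depends on a correlation that the protocol does not give, and for weight and BMI, where rho near 0.9 is a reasonable assumption, it is about 5% of variance. Some behaviours may also be analysed as categories: section 3.9.1 records activity as active or not, and fruit and vegetable intake appears under the chi-square tests. The variance ratios above do not apply to those. The power figures ignore group delivery and the exclusion of women below 60% attendance, so they illustrate the loss and are not forecasts for this trial. These limits stand too.

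Three stronger readings are tempting and not supported:

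- A reader might infer that weight, BMI, diet, knowledge and activity are compared only as change scores. The one-way ANOVA and chi-square are also listed. What is true is that neither is described as using baseline.
- A reader might infer that the five MetS components are protected because they are in the covariate-adjusted model. That model does not condition on baseline either, so the same loss applies to them.
- A reader might infer that smoking and alcohol are assigned an end-line chi-square. The protocol says only that they will be analysed; the test is an inference from its rule for categorical outcomes.

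**Conclusion.** The point holds as a matter of efficiency. No between-arm analysis in the Secondary outcomes or Data Analysis sections conditions on the outcome's own baseline value, although that value is collected.

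For continuous outcomes, adjustment would cut the variance by 35% at rho 0.3, 25% at 0.5, 15% at 0.7 and 5% at 0.9, relative to the change score. This assumes equal SDs at the two times and a rho that the documents do not supply. The gain is worth having for diet, activity and knowledge scores if their correlation is in the lower half of that range, and minor for weight and BMI. It covers the five MetS components as well, to a degree set by their own correlations.

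It does not show bias in any estimate or a fault in the primary outcome's sample size.

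**What to change.** In the Data Analysis section:

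1. For every continuous secondary outcome, including the five MetS components, make the between-arm analysis a linear model of the end-line value on arm plus the baseline value of that outcome. A mixed model with the two arms' baseline means constrained equal is an acceptable alternative. Report the adjusted difference with a 95% confidence interval. Use this in place of the repeated-measures ANOVA, the one-way ANOVA and the t test on change. If the existing mixed model is kept, write out its terms and add the baseline constraint.
2. For outcomes analysed as categories, use logistic regression on arm and baseline status where the numbers allow. State for each of diet, activity, smoking and alcohol whether it is analysed as continuous or categorical.
3. Keep mean change and the within-group paired tests as description only, and amend the sentence on mean change in Secondary outcomes to match.

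The cost is analysis wording only: no new measurements, visits or participants. The extra baseline term uses one degree of freedom, which is negligible at about 54 women per arm.

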#### **1.2 RATIONALE FOR PROPOSED TRIAL**

This study will determine the effect of a nutrition education, physical activity and motivation interviewing on metabolic syndrome indicators (WC, BP, HDL, TGS, blood sugar). Women in Uganda generally are instrumental in making key decisions in food selection (buying), processing and preparation for their families, it is necessary to provide them with essential education/knowledge to make appropriate decisions to prepare and provide food which is healthy, nutritious and adequate, in addition to encouraging them to adopt physical activity. These lifestyles changes may help women with MetS and their families to have improved outcomes. The intervention will therefore be designed to educate women with MetS on how to effectively utilize locally available foods and adopt physical activity in order to improve their metabolic profile.

The primary objective of the study is to assess the effect of interventions for preventing and managing Metabolic Syndrome, for informing policy.

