#### 2.2.2 Secondary objective

• To determine the effect of nutrition education, physical activity and motivational interviewing intervention on metabolic syndrome outcomes (blood pressure, high-density lipoprotein cholesterol, triglycerides, fasting blood sugar, waist circumference) and dietary intake, physical activity among females aged 15-49 years with metabolic syndrome in Wakiso district.

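### The MetS components are each put through several different between-group tests at p < 0.05 and none is named as the one that decides

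*Protocol*

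**What the plan says.** Section 3.6 of the Protocol names one primary outcome, the between-group change in MetS prevalence at 3 months. For the rest it says: "The secondary outcome will be the within - and between group variations in each of the following variable measured". The list that follows includes waist circumference under "anthropometric (weight, WC and BMI", and hypertension, glucose, triglycerides and HDL under the cardio-metabolic heading. Section 2.2.2 sets as the secondary objective the effect of the "intervention on metabolic syndrome outcomes (blood pressure, high-density lipoprotein cholesterol, triglycerides, fasting blood sugar, waist circumference"), together with diet and physical activity. Section 1.2 names the same five indicators.

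The Data Analysis text then prescribes:

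- a chi-square test for categorical outcomes, with the five metabolic risk factors listed among them;
- an independent-samples t test and ANOVA on cardio-metabolic parameters and on their variations, at baseline and end of intervention;
- a two-by-two group-by-time analysis, where a "repeated measures analysis of variance (ANOVA) will be performed for each dependent variable";
- a one-way ANOVA for group differences on the dependent variables, with Tukey's post hoc test after a significant finding;
- a paired t test within each group;
- a multilevel GLMM for blood pressure, waist, HDL, fasting glucose and triglycerides, adjusted for other factors.

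The threshold is stated once for all of these: "Statistical significance will be set at p < 0.05". The text does not say which between-group result decides an outcome.

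**The concern.** A p-value of 0.05 describes the error of one pre-chosen test. Here each MetS component can be compared between arms by end-of-intervention level, by change, by category and by an adjusted model. These can disagree, and the plan does not say which one stands. Whoever writes the report could then take whichever is significant, and the nominal 5% no longer describes the error behind that claim.

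This matters most for the five components because they make up the primary outcome and are themselves a stated objective. If the MetS comparison is negative, a significant result on one component by one of several routes is the likeliest positive statement to come out of the trial.

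**Working it through.** **Inputs from the Protocol.** Per-test level 0.05 (Data Analysis); sidedness is not stated, so two-sided is assumed. Two arms, two time points. Five components (sections 1.2 and 2.2.2). The Protocol states no familywise error rate, so there is no figure of its own to reproduce.

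**Inputs assumed.** Correlation r between baseline and endline of one outcome: 0.5. Correlation rho between outcomes: 0 to 0.8. The Protocol gives neither.

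**Step 1: which tests are really different.** With two groups, the one-way ANOVA on a given quantity is the t test on it (F = t squared). With two groups and two times, the group-by-time interaction is the t test on change. The named continuous-data tests therefore reduce to two distinct unadjusted ones: end-of-intervention level and change from baseline. The chi-square test on dichotomised factors and the adjusted GLMM are further routes. They are left out of the count below, so it is not inflated by them. Tukey's procedure compares pairs of groups within one outcome. With two groups there is one pair, so it adjusts nothing, and it never acts across outcomes.

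**Step 2: one outcome, two tests.** With equal variances at both times and no effect, the end-of-intervention and change statistics have correlation

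sqrt((1 - r)/2) = sqrt((1 - 0.5)/2) = 0.5.

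The probability that at least one of two standard normal statistics with correlation 0.5 exceeds 1.96 in absolute value is 0.091. That is 0.091/0.05 = 1.8 times the nominal level.

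**Step 3: five components, one test each.** If independent, 1 - 0.95^5 = 0.226. Simulation with equicorrelated normal statistics gives 0.18 at rho = 0.5 and 0.13 at rho = 0.8.

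**Step 4: five components, either test counts.** If independent, 1 - (1 - 0.091)^5 = 0.38. Simulation gives:

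| Between-outcome correlation | One test each | End-of-intervention or change |
|---|---|---|
| 0 | 23% | 38% |
| 0.5 | 18% | 31% |
| 0.8 | 13% | 22% |

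All are two-sided probabilities of at least one p < 0.05 among the five when the programme has no effect on any of them.

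**Step 5: what the undecided choice adds.** At rho = 0.5, moving from one named test to a choice of two takes the rate from 18% to 31%, an addition of 13 percentage points. Naming the deciding test removes that part. The remaining 13-23% comes from looking at five outcomes, and the exploratory label deals with it.

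**The case against.** The strongest reply is that handling of secondary multiplicity is often left to a SAP, that unadjusted secondary outcomes are common, and that the Protocol never promises 5% control across them. All of that stands, and the absence of a familywise method is not the point here. The point is a rule the Protocol does state: several distinct tests of the same outcome, one threshold, no deciding analysis. A SAP that named one would have to override this text.

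A second reply is that the t-test sentence ends with an after-before remark, so it may mean only the change comparison, and that the one-way ANOVA has no stated time point. This is a fair reading, and it makes the two-test figures conditional. But the sentence covers both the parameters and their variations, so the end-of-intervention reading is at least as open, and the text should not leave it open.

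A reader might go further and infer that all 14 or so listed secondary variables are confirmatory, and that a useless programme would show some effect 35-55% of the time. The documents do not support that:

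- The outcomes are labelled secondary beneath a single primary, and the sample size rests on MetS prevalence alone.
- The t tests are for cardio-metabolic parameters and the GLMM is for the five components. Smoking and alcohol may receive only a chi-square test.
- At a correlation of 0.5, 35% belongs to one test each and 55% to two tests each. These are two scenarios, not one range. At 0.8 the one-test figure is 20%.
- The remark in section 1.2 about informing policy is attached to the primary objective, not to isolated component results.

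Finally, the rates in the working count differences in either direction. Counting only favourable ones, with one test each, the five components give 12%, 9% and 6% at correlations 0, 0.5 and 0.8, against a nominal 2.5%.

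**Conclusion.** The point holds for the secondary outcomes that receive overlapping tests, above all the five MetS components. If either the end-of-intervention or the change test may count, the two-sided false-positive rate is about 9% for one continuous outcome. For at least one of the five it is about 31% (22-38%), against 13-23% with one test each. These figures rest on an assumed baseline-endline correlation of 0.5, assumed between-outcome correlations from 0.8 to 0, and the reading that both levels and changes are compared. The error rate of the primary comparison is unchanged. This should be corrected because it is cheap and the text invites selection, but it does not threaten the trial's main conclusion.

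**What to change.** In the Data Analysis section:

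1. Name one between-group analysis per outcome as the deciding one, for example the baseline-adjusted or the group-by-time contrast.
2. Drop the separate end-of-intervention t test, the one-way ANOVA and the Tukey step as decision tests. Describe any other retained comparison as supportive.
3. State that p < 0.05 is confirmatory for the primary outcome only, and that secondary outcomes are exploratory and reported as between-group differences with 95% confidence intervals.

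Mirror point 3 in the secondary outcomes text of section 3.6. If the sponsor wants to make formal claims on the five components, a Holm-adjusted family tested only after a significant primary result is an option, but it is not required. Its smallest p-value would face 0.05/5 = 0.01.

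The change is wording only, needs no new data or participants, and reduces the analysis work. The cost is that secondary results are claimed less strongly.
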